3. WORK PROPOSED

Overview: The study design for the present proposal is illustrated below. To obtain adequate power to detect a difference in prostate tumor apoptosis between the groups, the trial will require 30 patients per group. Based on our prior experience with the weight loss intervention we will be using in this trial, we are assuming a 15% dropout rate in the Weight Loss Group. Therefore, we are adding an additional 5 subjects to the Weight Loss Group to bring the total in this group to 35 and the total in the overall trial to 65.

Screening and Recruitment of Subjects - Minority Participation: Subjects will be recruited for the present trial from the VA Medical Center, Greater Los Angeles Health Care System. [name] conducts the urologic oncology clinic at the VA in which 130 new prostate cancer cases are diagnosed per year. Subjects with a new diagnosis of prostate cancer at the VA are offered standard therapies as well as the opportunity to participate in clinical trials. Subjects expressing interest in the weight loss trial will be given the consent form to review and the phone number of [name] research coordinator. Given the high prevalence of overweight and obese subjects (up to 70 % at our VA¹⁰), and given the high number of radical prostatectomy procedures performed at our VA (40/year), we anticipate no problem meeting our

recruitment goal of 65 subjects over 5-years. As well, given that 40-50% of men that undergo radical prostatectomy at the VA are AAM, we anticipate 40-50% of men in our clinical trials will be AAM.⁶² This is extremely important given the increased risk of obesity in AAM and the undue burden of increased morbidity and mortality of prostate cancer in AAM. For men randomized to the weight loss intervention group, the 4-9 week delay in radical prostatectomy has been shown not to increase the risk of biochemical recurrence.⁶³ However, we will not enter patients in this trial with a high risk of having advanced disease (Gleason Grade > 4+4) to avoid the potential risk (albeit extremely low) for progression during the weight loss intervention.

Inclusion Criteria:

1. Subject is overweight or obese (BMI > 25 kg/m²)
2. Patient with pathologically confirmed adenocarcinoma of the prostate and has elected to undergo radical prostatectomy
3. Able to adhere to physical activity intervention (able to walk for 10 minutes without rest)
4. Able to come to the VA CRC for study visits over 4-9 weeks (necessary if the subject is randomized to the weight loss intervention group)
5. Patient agrees to stop taking dietary or vitamin supplements (Lycopene***, Vitamin E, selenium, genistein, fish oil) or herbal supplements (e.g., saw palmetto, PC-SPES) prior to starting the dietary intervention.

Exclusion Criteria:

1. Gleason grade of prostate cancer > 4+5.
2. History of ever receiving androgen deprivation therapy or antiandrogen therapy
3. History of receiving finasteride* in the past 9 months
4. Patient receiving insulin** for diabetes mellitus
5. Current use of weight loss medications
6. Significant co-morbidities (i.e. cardiac, pulmonary, liver disease, ongoing alcohol/drug abuse)
7. Cardiac pacemaker

* Androgen deprivation therapy: Leuprolide, Goserelin. Antiandrogen therapy: Flutamide, Bicalutamide

** Changes in insulin levels may impact on the proposed biomarkers (IGF-1, IGFBP-1)

*** Lycopene has previously been shown to impact on apoptosis in prostate cancer tissue⁶⁴

Clinical Trial Flow Chart:

Activity	Screen											surgery
	wk -1 to 0	baseline	wk 1	wk 2	wk 3	wk 4	wk 5	wk 6	wk 7	wk 8	wk 9	
	V1	V2	V3	V4	V5	V6	V7	V8	V9	V10	V11	
Obtain Informed Consent	✓											
Review Inclusion/Exclusion	✓											
Medical Hx & Phys Exam	✓											
Concomitant Medications	✓ 		✓	✓	✓	✓	✓	✓	✓	✓	✓	
Waist-to-Hip measurement ³	✓	✓		✓		✓						✓
Weight	✓	✓	✓	✓	✓	✓	✓	✓	✓	✓	✓	
Give subject 3-Day Food Diary to complete		✓	✓	✓	✓	✓	✓	✓	✓	✓		
Randomization	✓											
DEXA Scan	✓											✓
Collect 3-Day Food Diary		✓	✓	✓	✓	✓	✓	✓	✓	✓	✓	
Serum Biomarkers/Bioassays ¹	✓											✓
Weight loss Intervention Visits ²		✓	✓	✓	✓	✓	✓	✓	✓	✓	✓	
Assess adverse events	✓	✓	✓	✓	✓	✓	✓	✓	✓	✓	✓	
Tissue collection for biomarkers												✓

Footnotes:

1. Fasting serum biomarkers/bioassays to be studied are IGF-1 and IGFBP-1 and the ex-vivo mitogenic and apoptotic activity of subject serum on LNCaP cells. Additional fasting serum studies will be insulin, PSA, and lipids.
2. The No Weight Loss Group has the same Baseline Visit procedures and Final Visit procedures (within 3-days prior to surgery) as the Weight Loss Group: Dexa Scan, fasting serum biomarkers, anthropometrics, and a 3-Day Food Diary.
3. At week 9 or Final Waist/Hip Measurement will be at the Final Visit Prior to Surgery.

Study Procedures: Subjects will have their first study visit at the VA Greater Los Angeles Healthcare System Clinical Research Center (CRC) which will include subject consent and review of the entry criteria. Once consent is obtained, a medical history and physical exam will be performed including height, weight, and measurement of waist to hip ratio (anthropometrics). The urologist's DRE and clinical stage will be recorded from the subject's urology note, and prostate needle biopsy pathology including Gleason grade and percent of cores with cancer will be recorded. A fasting serum specimen will be collected for biomarker studies. A DEXA scan will be performed (to determine lean body mass to calculate caloric intake for the weight loss program) and to determine percent body fat. The Subject will then return home and during the next week will keep a 3-Day Food Diary (Appendix 2). Subject's will be randomized within 3-days of their initial visit and contacted at home with the results of the randomization.

Randomization: If a subject meets all eligibility criteria, the following steps will occur:

1. The study coordinator will FAX the subject's initials, study ID, and date of visit to the junior statistician (to be named).
2. Within 24 hours the statistician will inform the research coordinator of the randomization result (weight loss vs. No Weight Loss Group) and date of randomization. The research coordinator will inform the study subject of the results and schedule subsequent study visits.
3. The randomization will use a permuted block design with 5 blocks of size 13 (7 weight-loss and 6 no weight-loss).

Control – No Weight Loss Intervention Group: After randomization to the control group, these men will proceed with radical prostatectomy as scheduled. They will have one additional visit to the VA CRC within 3 days prior to radical prostatectomy for measurement of weight, height, and waist to hip ratio, fasting blood will be collected for biomarkers and a DEXA Scan. During the week prior to the radical prostatectomy a 3-Day Food Record will be completed as well. We are doing this second visit in the control group to monitor for possible weight loss that these subjects may initiate on their own, although we do not anticipate this occurring to any significant degree. Subjects in the Control group will be given the phone number of the study coordinator to schedule their optional 5-8-week weight loss program after they have recovered from their surgery. This optional weight loss program is given as an incentive for their participation in the trial.

Weight Loss Intervention Group: Subjects randomized to the Weight Loss Group will receive an appointment to the VA CRC to meet with the research study coordinator and the study dietician to initiate the weight loss intervention. Subjects will receive one of two standard structured energy-restricted meal plans (1200, 1500, 1800 Kcal/day) using meal replacements and portion-controlled foods. Prescribed plans will be based upon resting energy expenditure and lean body mass as determined by DEXA scanning. The goal of the meal plan is to provide a total calorie intake incorporating 500-800 Calorie deficits per day. Since men will be provided with exercise regimens as well, they should experience a 1 to 2 pound weight loss per week during the weight loss intervention. Based on our experience in prior trials, we anticipate subjects will lose 4-6% of their body weight over 5-8-weeks as a result of the weight loss intervention.

Subjects will have weekly visits with the study dietician until the time of the radical prostatectomy. [name] or her associates will oversee each of these visits with the study dietician. The subject will receive instruction on recipes, ideas and places for food shopping, education on healthy food preparation, and preparation of meal replacements. Recommended diets will

contain 20-25% energy from fat, 15-20% from protein and 50-65% from carbohydrates largely from fruits and vegetables with some whole grains. Fiber recommendations will be a total of 25 grams/day from fruits, vegetables, legumes, and high fiber cereals.

Subjects will be counseled by [name] or her associates on performing 1 hr of exercise/day including aerobic, resistance, and flexibility activities. As an exercise incentive, subjects will be given a pedometer and exercise an log (Appendix 3) to complete and results will be reviewed with the dietitian at each visit. Subjects will be weighed at each visit and waist to hip ratio will be measured at the Screening or Baseline, Weeks 2, 4 and 9. Following the 4-9-week weight loss intervention and within 3 days prior to radical prostatectomy, weight and waist to hip ratio will again be measured, fasting serum will be collected for biomarkers, and a DEXA Scan will be performed to assess the change in body fat and lean body mass as a result of the intervention. In addition, during this week subjects will also complete a 3-day Food Diary to assess dietary and caloric intake to bring with them for their final study visit prior to surgery.

At each study visit, we will go over concomitant medications, adverse events and we will assess subjects for fatigue as well as the ability to perform their usual daily tasks (functional ability). If subjects have significant loss of strength or daily function, we will take them off protocol and have them re-evaluated in the preoperative clearance clinic at the West Los Angeles VA to make sure they can safely undergo radical prostatectomy.

Post-Prostatectomy Follow-up: Subjects in the Weight Loss Group will have scheduled visits at 3 months and 9 months post-op to assess for adverse events, and to measure body weight to determine if subjects maintain the weight loss achieved during the pre-operative intervention. If they are unable to come to the VA, this visit can take place over the phone. This will be the same for the Control subjects.

Radical Prostatectomy–Tissue Collection: At the time of prostatectomy, frozen tissue blocks of benign prostate tissue and prostate carcinoma will be obtained immediately following surgery. Frozen sections will be evaluated by a pathologist to ensure the quality of the specimens and verify if the specimen represents benign or malignant tissue. Fresh tissue will be embedded in OCT (polyvinyl alcohol and polyethylene glycol), 'snap frozen', and stored at -80°. The remainder of the tissue will be fixed in 10% neutral buffered formalin and embedded in paraffin for routine histology and immunohistochemistry studies. The amount of fresh tissue obtained will vary depending on the size of the carcinoma, but our experience has shown that at least one 1.0 x 0.5 x 1.0 cm tissue block representative of the carcinoma, and a similar sized block of benign prostate tissue can be retrieved from most prostatectomy specimens. At the time of radical prostatectomy a sample of fat from the anterior surface of the prostate, a sample of subcutaneous fat and fat from the inner abdominal wall will be collected. Half of the tissue will be flash frozen and used for genomic and proteomic analysis. The other half will be cultured at 37 degrees centigrade in M199 media and the conditioned media will be harvested and used to quantify secreted inflammatory cytokines such as IL8 and IL6.

Serum and Plasma Studies-Overview: Serum insulin, Free and Total Testosterone, Estradiol, Leptin, IGF-1, IGFBP-1, PSA, lipids, ex-vivo mitogenic bioassay, and the ex-vivo apoptosis assay will be performed at baseline and prior to radical prostatectomy in all subject in the Weight Loss Group and control group. We are measuring PSA levels given that PSA represents an established tumor marker of disease progression in prostate cancer and weight loss may potentially decrease the PSA. PSA levels will also be measured in subjects in the control and Weight Loss Groups post-operatively every 6-months (for the 10-year study duration) as is routine in our GU Oncology clinic at the VA. White blood cells will be collected from the buffy

coat, RNA extracted, and PCR arrays will be performed to quantitate inflammatory cytokines and chemokines. Subject weights will also be recorded at these visits.

Ex-Vivo Bioassays: The ex-vivo mitogenic and apoptosis bioassay will be performed in the laboratory of [name]. These bioassays are designed to test the presence of serum factors affecting the proliferation and apoptosis of androgen dependent (LNCaP) prostate cancer cells by substituting FBS in the medium with human serum collected before and after an intervention.

Rationale for prostate cancer tissue analysis: Weight-loss may affect prostate cancer through numerous mechanisms involving both primary and secondary effects (through changes in serum IGF molecules or other factors). These changes may influence the expression of mRNA of key molecules, the levels of proteins expressed in cancer cells, or the phosphorylation/activation state of key growth and survival signaling cascades. Our primary goal in this project is to identify proliferative and apoptotic changes in prostate cancer tissue in response to weight loss. We will also focus our studies based on our prior observations in preclinical xenograft models that showed diet-induced changes in IGF1 gene expression and protein levels, and reduction in the phosphorylation of the IGF-1 receptor in prostate cancer tissue. We will follow these with additional related studies of down-stream survival molecules such as Akt/phospho-Akt, activated caspase-3, BCL2, and BAX. Initial findings will guide us regarding the performance of these secondary outcome measures.

Immunostaining and Interpretation: Immunostaining of paraffin embedded pretreatment prostate needle biopsy specimens and malignant tissue from radical prostatectomy specimens will be performed using ki67 monoclonal antibodies (DAKO) and a TUNEL assay (BioVision). The cancer tissue with the highest Gleason grade will be analyzed in a blinded fashion by counting 300 cancer cells per slide. Our main objective (Objective 1 of this proposal) will be to compare the percent of cells staining positive for ki67 and TUNEL between the Control Group-No Weight Loss and Weight Loss Group (controlling for Gleason grade). We will also compare the percent of cells staining for ki67 and TUNEL in the prostate needle biopsy specimen relative to the prostatectomy tissue (also matching for Gleason grade). In addition, we will perform correlation analysis to determine if weight loss correlates with proliferation and apoptosis. We hypothesize that with increasing weight loss there will be decreased ki67 staining and an increasing percentage of cells with TUNEL staining. To further evaluate the effect of weight-loss on prostate tumor staining of the IGF signaling cascade we will analyze immunostaining of phospho-IGF-1R (using a Cell Signaling antibody) and phospho-Akt (Cell Signaling). We will also evaluate for earlier stages of apoptosis as measured by activated caspase-3 (Oncogene). If we detect changes in apoptosis, we will also stain for BAX and BCL2 using antibodies from R&D. If we detect changes in proliferation as measured by ki67 staining, we will also stain for Mcm-2 (which has been shown to be a prognostically important prostate cancer proliferation marker) using antibodies from R&D.⁶⁶

Prostate Cancer tissue RNA and Protein Analysis: For Western analysis, equal amounts of protein from the tumor tissue lysates will be evaluated by 8% SDS-PAGE analysis. Beta Actin antibodies (Cayman Chemicals, MI) will be used for loading control. Membranes will be developed using the ECL system (Amersham). Primary antibodies to total and phosphorylated IGF1 receptor (Cell Signaling) will be used. As a secondary aim, if we find that weight loss significantly impacts on the IGF-1 axis proteins as hypothesized above, we will perform analysis of total and phosphorylated Akt (Cell Signaling) which is known to be activated downstream from the IGF-1 receptor. In the event that increased apoptosis is observed in the experimental Weight Loss Group, we will also immunoblot for BAX and BCL2 using R&D antibodies.

Quantitative real time PCR analysis (QRT-PCR): Total RNA from the frozen tissue will be extracted using the RNeasy kit (Qiagen) and checked for its purity and total RNA content. QRT-PCR will be performed on all samples to determine the expression of IGF-1, the apoptosis-related genes (BCL2, BAX) and the housekeeping gene Beta-actin. cDNA will be synthesized using the First Strand cDNA Synthesis kit for RT-PCR (Roche). Gene-specific primers and probes were designed and synthesized by the as previously published and are not listed here. PCR will be performed (in triplicates) in a LightCycler thermal cycler (Roche) using previously published conditions and amplification programs. A negative control without a cDNA template will be run simultaneously with every assay. Standard curves will be obtained using serial dilutions of the beta-globulin gene (DNA Control Kit; Roche). The concentration of each gene product will be determined on the basis of a kinetic approach using the lightcycler software (Roche) and normalized for *ACTB*. When comparing gene expression and protein levels between the groups, we will match the Gleason grade of the tissue. All of the above methods are fully operational in our laboratory.

Proteomics/Genomics: We plan to further study the molecular nature of the weight loss-induced changes in the tumor proteome through gene array and proteomic approaches coupled with confirmatory protein and RNA analyses.

Statistical Analysis

Statistical Design: The statistical design of this study is a randomized repeated measures utilizing random mixed block sizes known only to the statistician constructing the randomization list to assign subjects to two study arms in a ratio of 7:6, weight loss to no weight loss.

Sample Size Determination: An evaluable sample of at least 60 subjects (no weight loss=30, weight loss=30) is expected to provide 80% power to detect an effect size of 0.74 using a two group t-test with a 0.050 two-sided significance when comparing the apoptotic index (primary outcome variable) in the radical prostatectomy malignant epithelium between the weight loss and no Weight Loss Group. The apoptotic index will be measured in the malignant epithelium with the highest Gleason grade. To account for a post-randomization attrition rate of up to 15% in the Weight Loss Group, a total of 35 subjects will be randomized to the Weight Loss Group, thus bringing the total sample size to 65 subjects. Kim et al. observed an effect size of 1.74 on apoptotic index using a nutritional intervention in a similar study.⁶⁴

Data Analysis: Data analyses will be performed on randomized subjects who complete the study. All parameters measured will be summarized descriptively. The number of subjects, mean, standard error of the mean, median and min-max values will be presented for continuous parameters and the number and percentage of subjects in each category will be presented for categorical parameters. No imputation of missing data is planned. Demographic and baseline characteristics will be summarized using descriptive statistics overall and by treatment group to assess baseline comparability. Treatment groups will be compared using the appropriate nonparametric tests for categorical parameters and analysis of variance models for continuous parameters.

Primary Outcome Variable: The primary outcome variable is apoptotic index of the highest Gleason grade malignant epithelium in the radical prostatectomy specimen. The primary objective is to compare the mean apoptotic index between the Weight Loss Group and the Control Group-No Weight Loss. The two independent sample t-test will be used to compare the index between the groups. If the index is non-normally distributed we will use the Wilcoxon rank sum test. Next, linear regression models will be constructed to test whether the treatment effect

is significant after controlling for Gleason grade, stage and any demographic factors that are significantly different between the groups.

Secondary Outcome Variables: The secondary outcome variables are: the proliferative index in prostate cancer epithelium obtained from the radical prostatectomy specimen, the change in apoptotic and proliferative indices of malignant epithelium between the diagnostic prostate needle biopsy and corresponding radical prostatectomy, the change (baseline vs post-intervention) in serum IGF-related analytes: IGF-1 and IGFBP-1, the ex-vivo mitogenic and apoptotic activity of patient sera on LNCaP cells, and the change in body weight and percent body fat by DEXA over 4-9-weeks.

Secondary Statistical Analyses: The statistical methods for these analyses will be analysis of variance (ANOVA), linear regression, and correlation analysis. ANOVA will be used to determine if the serum biomarkers (IGF-I, IGFBP-1, proliferation and apoptosis bioassays) change over the course of time. These models will include a term for time, treatment (weight-loss versus no weight loss) and the time by treatment interaction effect. We will also construct ANOVA models for weight and body fat over time to determine if the treatment by time effect (intervention effect) is significant. Next, linear regression models will be constructed for each biomarker to assess the factors that predict change in that marker. Predictors will include actual weight loss (percent change), group, grade, PSA, percent body fat, and demographic factors. These models will allow us to assess the direct effect of weight loss on each of the serum biomarkers and allow for the assessment of whether weight change or intervention is the primary factor predicting change in the biomarkers. This assessment is required due to the fact that the intervention will have varying effects on weight based on the amount of subject compliance with the weight loss regime. Regression models will also be constructed to compare the groups with respect to the pre-prostatectomy biomarkers and the tissue markers and the between group tissue markers (apoptosis, Ki67 staining). A separate model will be constructed for each marker including the predictors of group, grade, PSA, percent body fat and demographic factors. Next, we will construct regression models to determine if the biomarkers, or change in biomarkers, affect the post-op pathology. Ordinal regression will be used for post-op pathology. These models will include terms for the demographic factors and for each of the biomarkers. Since there are a large number of biomarkers we will first construct single biomarker models which will include the covariates for each outcome and then combine together all significant markers into multiple regression models. Finally, we will use the Spearman correlation to test for correlations between pre-prostatectomy biomarkers and the tissue markers. This analysis will specifically address **Objective 3** of the proposal, that being to determine if a correlation exists between serum biomarkers and tissue biomarkers. The Spearman correlation is a non-parametric rank based correlation measure that does not depend on the assumption that the markers are normally distributed.

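### The recruitment text bars Gleason above 4+4, but exclusion criterion 1 bars only above 4+5, so the two limits disagree on whether a Gleason 4+5 man may enter

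*Combined protocol and SAP*

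**What the plan says.** All of the relevant text is in Section 3 (Work Proposed) of the combined protocol and SAP.

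- **Screening and Recruitment of Subjects.** The protocol states "we will not enter patients in this trial with a high risk of having advanced disease (Gleason Grade > 4+4", and gives the purpose: "to avoid the potential risk (albeit extremely low) for progression during the weight loss intervention". The sentence just before places a 4-9 week postponement of surgery in the weight loss arm and cites a study as evidence that this does not worsen biochemical recurrence. The grade limit follows as a qualification of that reassurance.
- **Exclusion Criteria, item 1.** The limit here is "Gleason grade of prostate cancer > 4+5". No other inclusion or exclusion item restricts grade.
- **Study Procedures.** At the first visit, "prostate needle biopsy pathology including Gleason grade and percent of cores with cancer will be recorded". Randomization comes afterwards.
- **Randomization.** "If a subject meets all eligibility criteria, the following steps will occur".
- **Control group.** These men go to surgery on their existing schedule, so the added wait falls on the weight loss arm.

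**The concern.** Two current statements of one entry rule give different answers for the same man. The stricter one is the only grade-based protection that the protocol offers for postponing cancer surgery, and it is absent from the numbered list that site staff would normally check. If staff work from that list, a man whom the recruitment text describes as too high-risk to enter could be assigned to wait. A monitor reading both statements could not say whether a Gleason 4+5 entrant is eligible or a deviation.

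**Working it through.** **Step 1: the two limits side by side.** The sign is not defined for a pair of Gleason patterns. It can be read by sum, or by primary pattern first and secondary pattern second. Taking patterns 3 to 5, the pairs 3+3, 3+4 and 4+3 are allowed by both limits on both readings. The rest are:

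| Biopsy pattern | Sum | Recruitment text, by sum (bars > 8) | Exclusion 1, by sum (bars > 9) | Recruitment text, by primary pattern | Exclusion 1, by primary pattern |
|---|---|---|---|---|---|
| 3+5 | 8 | allowed | allowed | allowed | allowed |
| 4+4 | 8 | allowed | allowed | allowed | allowed |
| 5+3 | 8 | allowed | allowed | barred | barred |
| **4+5** | 9 | **barred** | **allowed** | **barred** | **allowed** |
| **5+4** | 9 | **barred** | **allowed** | barred | barred |
| 5+5 | 10 | barred | barred | barred | barred |

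The limits disagree on 4+5 under either reading, and on 5+4 only if the sign is read by sum. The conflict therefore does not depend on how the sign is interpreted.

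**Step 2: does anything reconcile them?** Inclusion criterion 2 asks only for confirmed adenocarcinoma and an elected prostatectomy. The other exclusions concern prior or current drugs, comorbidity and a pacemaker. Both limits stand in current text, and neither is marked as replacing the other.

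**Step 3: recruitment cost of the stricter limit.** Inputs from the recruitment text are 40 prostatectomies a year, 5 years, up to 70% overweight or obese, and a target of 65.

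- Pool: 40 × 5 × 0.70 = 140 men at most.
- Uptake needed now: 65/140 = 46.4%.
- The share of candidates in the gap is not given, so it is assumed:

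| Assumed share removed | Pool left | Uptake needed |
|---|---|---|
| 1% | 138.6 | 65/138.6 = 46.9% |
| 5% | 133 | 65/133 = 48.9% |
| 10% | 126 | 65/126 = 51.6% |

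The 140 is a maximum: 70% is itself an upper figure, and men lost to the other exclusions (insulin use, comorbidity, finasteride, prior hormone therapy) have not been taken off. Each uptake figure is therefore a minimum. With an assumed pool of 100, removing 10% moves the requirement from 65/100 = 65% to 65/90 = 72%.

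**The case against.** **The risk is small and the delay is said to be safe.** The recruitment text says both. It then imposes the grade limit anyway, so the reassurance was not treated as sufficient above 4+4. What stands is that no harm can be inferred. The cited study cannot be examined here, and the documents do not show whether the delay is safe or unsafe for Gleason 4+5.

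**It may be a single misread character.** If exclusion 1 was printed as 'at least 4+5', it would agree with the recruitment text on both readings. Nothing in the available text shows this, but checking the criterion in the source document would settle it.

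**A reader might infer that the numbered list decides, so that Gleason 4+5 men will be randomized.** The documents do not go that far. The Randomization text refers to all eligibility criteria without confining these to the list, and the recruitment statement is itself worded as an entry rule. A site that applied both would bar 4+5. The supportable statement is that a coordinator using the list alone could admit such a man.

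**A reader might also infer that the primary comparison is compromised**, because the outcome is the "apoptotic index of the highest Gleason grade malignant epithelium in the radical prostatectomy specimen" and no rule covers ineligible entrants. This does not follow. The entry limit concerns biopsy grade and operates before randomization, so either limit leaves the randomized comparison unbiased. The planned regression also adjusts for Gleason grade.

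**Conclusion.** The eligibility threshold is wrong as written. The protocol states two Gleason limits for one rule, and Gleason 4+5 falls between them on any reading of the sign. The consequence is a possible failure of the protocol's own safeguard against progression during a 4-9 week surgical delay, together with an eligibility rule that cannot be monitored consistently.

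This conclusion rests on comparing two statements and needs no assumption about grade distribution. The number of men who might be affected cannot be derived from the documents, and any figure for it would only restate an assumed share. The documents also do not show which limit the sponsor intends.

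**What to change.** State one limit in both places.

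- **To apply the stated safeguard:** replace exclusion 1 with *Biopsy Gleason sum of 9 or 10 (4+5, 5+4 or 5+5)*, judged on the biopsy grade recorded at the first visit, before randomization. This matches the recruitment text read by sum and removes the unclear sign. It admits 5+3; if the sponsor means a primary-pattern rule, 5+3 should be listed as well.
- **If the wider limit is intended:** correct the recruitment text, explain why the 4-9 week delay is acceptable for Gleason 4+5, and say how 5+4 is treated.

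Either route changes a few words and needs no new data collection. The cost of the first is the loss of Gleason 9 candidates whom the list now admits: 4+5 alone if the sign was being read by primary pattern, or 4+5 and 5+4 if by sum. Required uptake is at least 46% now and would be at least 52% if an assumed 10% of the pool were removed.

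### The supplement stop is timed only to the start of the dietary intervention, which control men do not reach before surgery, so lycopene use could differ by arm on the primary outcome

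*Combined protocol and SAP*

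**What the plan says.** All of this is in section 3, Work Proposed.

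- **Inclusion Criteria, item 5.** Men agree to stop lycopene, vitamin E, selenium, genistein, fish oil "or herbal supplements (e.g., saw palmetto, PC-SPES) prior to starting the dietary intervention". No other time point is given, and no end of the restriction is stated for either arm.
- **Footnote to lycopene in the same list.** "Lycopene has previously been shown to impact on apoptosis in prostate cancer tissue".
- **Control – No Weight Loss Intervention Group.** "After randomization to the control group, these men will proceed with radical prostatectomy as scheduled". These men receive the coordinator's number to "schedule their optional 5-8-week weight loss program after they have recovered from their surgery". They have one further visit, within 3 days before surgery.
- **Clinical Trial Flow Chart, footnote 2.** The control group is said to share the baseline and final visit procedures of the Weight Loss Group. The footnote then names them: "Dexa Scan, fasting serum biomarkers, anthropometrics, and a 3-Day Food Diary".
- **Weight Loss Intervention Group.** Visits are weekly until surgery. The closing text of that part says concomitant medications are gone over at every study visit.
- **Primary Outcome Variable.** The outcome is the apoptotic index in the highest-grade malignant epithelium of the prostatectomy specimen.
- **Sample Size Determination.** The design assumes 30 evaluable men per arm and an effect size of 0.74. As a benchmark, a cited trial (reference 64, the same as in the lycopene footnote) "observed an effect size of 1.74 on apoptotic index using a nutritional intervention in a similar study".

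**The concern.** A rule meant to keep an outside influence off the primary endpoint should bind both arms over the same period. Here the trigger is an event in one arm only. A control man who follows the wording exactly could stay on lycopene until his prostate is removed, while a Weight Loss man must have stopped when his program began.

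Exposure to something the protocol itself links to tissue apoptosis could then depend on the arm. Randomization does not protect against this, because the difference would arise after allocation. If lycopene raises apoptosis, continued use in controls alone would lift the control mean and shrink the contrast. The secondary outcome of change in apoptotic index from biopsy to prostatectomy would be exposed in the same way.

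The planned t-test and the regression models contain no supplement term. If use is not recorded at the control arm's last visit, an imbalance could be neither seen nor examined afterwards.

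**Working it through.** **Step 1. Does the trigger occur in both arms before the endpoint?**

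| | Weight Loss Group | Control group |
|---|---|---|
| Agrees to criterion 5 before randomization | Yes | Yes |
| Starts the dietary intervention before surgery | Yes | No; offered only after recovery |
| Literal stop time before tissue collection | Start of program | None |
| Stated end of the restriction | None | None |

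**Step 2. Is use recorded alike?** The flow chart ticks concomitant medications at screening, which all men attend, and at the weekly visits through week 9. For the control final visit, both the list in footnote 2 and the control-arm paragraph omit the item. The opening of footnote 2 (shared procedures) and the every-visit sentence could be read to include it, but that sentence sits in the Weight Loss Group text. The control final visit is therefore ambiguous. No passage says that supplements are recorded under concomitant medications in either arm.

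**Step 3. Reproduce the plan's power.** Inputs from Sample Size Determination: 30 per arm, effect size 0.74 (so SD = 1), two-sided alpha 0.05, two-group t-test. The noncentral t distribution gives power of 80.5%, and the n required for 80% is 29.66, rounded up to 30. The plan's figure reproduces.

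**Step 4. Illustrate a one-sided exposure.** Let f be the share of controls who continue a pro-apoptotic supplement and e its effect in SD units. Assume a true weight loss effect of 0.74, complete stopping in the Weight Loss Group, and SD held at 1. Then

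contrast d = 0.74 − f × e.

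The documents give no value for f, so 5%, 10% and 20% are assumed (1.5, 3 and 6 of 30 men). For e, 0.74 is assumed as a moderate case, and 1.74 (the cited study) serves as an upper case.

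| e | f | f × e | d | Power | Power with mixture variance |
|---|---|---|---|---|---|
| any | 0 | 0 | 0.740 | 80.5% | 80.5% |
| 0.74 | 5% | 0.037 | 0.703 | 76.3% | 75.8% |
| 0.74 | 10% | 0.074 | 0.666 | 71.8% | 70.7% |
| 0.74 | 20% | 0.148 | 0.592 | 61.6% | 59.8% |
| 1.74 | 5% | 0.087 | 0.653 | 70.1% | 67.1% |
| 1.74 | 10% | 0.174 | 0.566 | 57.8% | 52.5% |
| 1.74 | 20% | 0.348 | 0.392 | 32.1% | 26.8% |

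The last column allows for the extra spread among controls when some are exposed and some are not. Control variance is v = 1 + f(1 − f)e², and d is divided by √((1 + v)/2). For f = 20% and e = 1.74: v = 1 + 0.16 × 3.0276 = 1.484, √(2.484/2) = 1.114, and 0.392/1.114 = 0.352.

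**The case against.** The best defense is that criterion 5 is an inclusion criterion. Every man agrees to it before he knows his arm, and only men who meet all criteria are randomized. Criterion 4 says expressly that it matters for men allocated to weight loss; criterion 5 carries no such limit. The reason given for lycopene applies equally to both arms. On an ordinary reading, this is a loosely timed rule for everyone. That stands as a reading of intent. It does not supply a stop time for control men, because what they agree to is timed to an event they do not reach before surgery.

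A reader might also infer more than the documents support:

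- *That control use is unrestricted and unchecked.* This is too strong. Concomitant medications are ticked at screening for all men, and footnote 2's opening and the every-visit sentence may cover the control final visit. What can be said is that neither control list names the item.
- *That Weight Loss men are asked weekly about supplements.* The text refers to concomitant medications; the inclusion of supplements would be an inference.
- *That the listed products are all pro-apoptotic.* The documents claim an effect on apoptosis for lycopene only, and the footnote gives no direction.
- *That 1.74 SD is the effect of a supplement.* It is attributed to a nutritional intervention, and the title of reference 64 concerns tomato sauce consumption. It can serve only as an upper case.

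**Conclusion.** The point holds as a gap in the rule's timing, with a less certain gap in how use is recorded. Criterion 5 has one time anchor, and control men do not reach it before the primary endpoint tissue is collected. Lycopene exposure could therefore differ by arm. The documents do not show that it does or will.

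The direction is conditional: toward no difference if lycopene raises apoptosis and is continued only in controls. The size cannot be derived, because supplement use at entry is not given and no supplement effect is stated. The power range of 62% to 76% (assumed 0.74 SD) or 32% to 70% (1.74 SD) is an illustration over 5% to 20% continuing use, with full stopping in the other arm. The 32% figure in particular is not an estimate of this trial's power. The case for acting rests on the protocol's own link between lycopene and its primary outcome, and on how little the correction costs.

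**What to change.** 1. Reconcile criterion 5 with the control-arm text, so that the same supplement requirement is timed to an event both arms share (randomization is one candidate) and applies to both arms up to tissue collection. The length of any supplement-free period is for the investigators.
2. List a concomitant medication and supplement question explicitly among the procedures of the control arm's existing final visit before surgery, and word the Weight Loss Group item the same way, so that use is recorded alike.
3. State in the analysis section that recorded use will be summarized by arm and examined in a sensitivity analysis of the apoptotic index. This is supportive only, since use is observed after randomization.

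The question within 3 days of surgery records use but cannot prevent it, so the first change is the one that protects the comparison. The cost is one reworded criterion, one question at a visit that already takes place, and a sentence in the analysis section.
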